**Table 8: Analysis Visit Windows for Glucose Tolerance Test, HbA1c, Bone Markers, and Lipid Panel**

Scheduled Visit	Target Study Day	Analysis Window (Study Day Range)
Week 24	168	84 to (first dose date in OL period)
Month 12	336	252 to (first dose date in OL/DB period)

## 6.8. Handling of Missing Data

### 6.8.1. Start Dates for Adverse Events

For the purpose of estimating the time of the event in relationship to study drug (ie, study day), missing and incomplete (“partial”) dates for AEs will be imputed using the following algorithm. For start dates that are missing day and month: impute 1st January, unless the year is the same as the first dose of study drug, in which case the start date will be imputed to the date of first dose of study drug. For start dates that are missing day alone: impute to the 1st of the month unless the month and year are the same as the first dose of study drug, in which case the start date will be imputed to the date of first dose of study drug. There will be no imputation for AE stop dates.

### **6.8.2. Start and Stop Dates for Concomitant Medications**

To handle missing/partial dates for concomitant medications, the following algorithm will be employed to derive the time of medication usage relative to study drug (ie, study day). For start dates that are missing day and month: impute 1st January, unless the year is the same as the first dose of study drug, in which case the start date will be imputed to the date of first dose of study drug. For start dates that are missing day alone: impute 1st of the month unless the month and year are the same as the first dose of study drug, in which case the start date will be imputed to the date of first dose of study drug. For stop dates that are missing day and month: impute 31st December, unless the year is the same as the last dose of study drug, in which case impute to the date of last dose of study drug. For stop dates that are missing day alone: impute to the last day of the month unless the month and year is the same as the last dose of study drug, in which case impute to the date of last dose of study drug. If any of the above imputations result in a start date that is later than an observed (not imputed) medication stop date, the start date will be imputed as the stop date. Likewise, if an imputed stop date is earlier than an observed (not imputed) start date, then the stop date will be imputed as the start date.

If a medication is marked as “ongoing” at the time of the subject’s discontinuation from study, or if the subject is lost to follow-up, the stop date for the medication will be imputed to the subject’s end of study date.

### **6.8.3. First and Last Study Drug Dose Dates**

Missing and incomplete (“partial”) dates for first and last study drug dose dates will be imputed for the purpose of estimating exposure and defining treatment periods. Missing dates will not be imputed for subjects when the subject is known to have not taken at least one dose of study drug, as documented by the site in the study drug dosing electronic case report form (eCRF).

The imputation rules for first dose date are as follows:

- If the date is completely missing or if both the day and month are missing, the date will be imputed as the randomization date
- If only the day is missing, the date will be imputed as the randomization date if the month and year match the month and year of the randomization date; if the month or year occur after the randomization date, the missing day will be imputed as the first day of the documented month.

If the date of the last dose of study drug is missing, then the last dose date will be imputed as the earliest of:

- The end of treatment date
- The last visit prior to study discontinuation.

### **6.9. Coding Dictionaries**

Medical history and AEs will be coded using the Medical Dictionary for Regulatory Activities (MedDRA, version 26.0). Prior and concomitant medications will be coded using the World Health Organization (WHO) Drug Dictionary (March 2021 B3 Global version).

## 6.10. Impact of COVID-19 Pandemic

This section describes analyses and summaries that will be produced to help determine the potential impact of the COVID-19 pandemic on the study conduct/data and additional details regarding how data that is potentially impacted by the COVID-19 pandemic will be handled in the analysis plan. It is in alignment with the guidance put forth by the US Food and Drug Administration (FDA; Conduct of Clinical Trials of Medical Products During the COVID-19 Public Health Emergency [March 2020, updated January 2021]) and European Medicines Agency (EMA; Points to consider on implications of Coronavirus disease [COVID-19] on methodological aspects of ongoing clinical trials [March 2020]).

To help understand the impact of the COVID-19 pandemic on the clinical trial data, the following listings will be generated:

- A listing of all subjects affected by the COVID-19 pandemic. The listing will identify subjects who experience at least one of the following situations due to the COVID-19 pandemic (additional situations may be included):
  - Discontinued study drug or withdrew from study
  - Presumed or confirmed diagnosis of COVID-19
  - Had at least one COVID-19 pandemic-related major protocol deviation
  - Missed at least one study visit or assessment
  - Required at least one assessment to be collected using a method other than that defined in the protocol (eg, remotely)
  - Had at least one known study drug interruption
- A listing of subjects who discontinued study drug and/or withdrew from study due to the COVID-19 pandemic, which will include the specific reasons.
- A listing by subject of visits and assessments affected by the COVID-19 pandemic (eg, missing, partial, collected remotely).

The MedDRA standardized MedDRA queries (SMQ) of COVID-19 will be utilized to retrieve preferred terms (PTs) pertaining to COVID-19 to identify subjects with a presumed or confirmed diagnosis of COVID-19.

Further classification and summaries of protocol deviations related to the COVID-19 pandemic are detailed in Section 7.2.

Additional summaries may be generated to address the potential impact of the COVID-19 pandemic on the efficacy and safety data, as needed, based on ongoing data review or during the final analysis of study data in each of study periods.

## 7. STUDY POPULATION

### 7.1. Disposition

The summary of subject enrollment and disposition in the DB period will be displayed by DB treatment group (as defined in Section 6.1) as well as all subjects combined.

The table will include:

- The total number of subjects who provided informed consent and were screened (provided in table footnote)
- Number randomized (within column header)
- Number received study drug
- Number completed planned study drug through Week 24
- Number completed study through Week 24
- Number who did not complete study drug through Week 24, including reasons for early discontinuation of study drug
- Number who did not complete the study through Week 24, including reasons for early termination from the study

The summary of subject disposition in the OL period will be displayed by OL treatment group (as defined in Section 6.1) based on the number of subjects in the OL safety analysis set (within column header).

The table will include:

- Number who received study drug in the OL period
- Number who completed planned study drug through Month 12
- Number completed study through Month 12
- Number who did not complete study drug through Month 12, including reasons for early discontinuation of study drug
- Number who did not complete the study through Month 12, including reasons for early termination from the study

A summary of the number and percentage of subjects classified as Completers, Retrieved Dropouts, Non-retrieved Dropouts, and On Drug-Missing Endpoint Subjects (as defined in Section 6.4) for each of the primary and key secondary endpoints will be presented by treatment group for the DB period.

A listing of randomized subjects at Day 1 will also be provided and will include subject ID, informed consent date, randomization date, stratification factors, and randomized treatment group.

A summary of randomization by study site will be presented. This summary will display the number of subjects randomized to each treatment group by site.

A listing of lot numbers used in the study will be provided.

## 7.2. Protocol Deviations

Protocol deviations described in the study-specific Protocol Deviation Handling Plan (PDHP) will be entered into the clinical trial management system. Prior to database lock, all major protocol deviations that have been entered into the clinical trial management system will be exported to a file and integrated into the study data.

A protocol deviation that is classified as “major” is a deviation that has impacted or may significantly affect a subject’s rights, safety, or well-being, or is likely to have a significant impact on the primary or key secondary efficacy endpoint(s) for at least one subject. An assessment of protocol deviations will be performed by a committee composed of NBI Clinical Development study team members on an ongoing basis and prior to database lock and unblinding at the end of the DB period. At the time of NBI protocol deviation review, a major protocol deviation may be further classified as an IPD (Important Protocol Deviation) based on the magnitude of the deviation. An IPD is defined as a protocol deviation that may significantly impact the completeness, accuracy, and/or reliability of key study data or that may significantly affect a subject’s rights, safety, or well-being. Examples of what constitutes an IPD are listed in the PDHP. The above review will also be performed prior to database lock at the end of the OL period. The summaries described below will be produced for both treatment periods.

A summary of the number and percentage of subjects with IPDs by deviation category will be presented by treatment group and overall. The summary will be repeated for the subset of IPDs that are related to the COVID-19 pandemic.

All major protocol deviations will also be presented in a data listing. Any major PDs related to the COVID-19 pandemic or major PDs classified as IPDs will also be flagged in the listing.

## 7.3. Demographic and Baseline Characteristics

Demographics, baseline characteristics, and stratification factors (as entered into IRT) at study entry will be summarized descriptively by DB treatment group and overall using the FAS. The following variables will be summarized:

- Demographics:
- age (years)
- age categories (18-25 years; 26-35 years; 36-45 years; 46-55 years; 56-65 years; 66-75 years;  $\geq 76$  years)
- sex (based on the eCRF)
- ethnicity
- race
- region (OUS vs US)
- 

Baseline characteristics (based on eCRF unless otherwise specified):

- height (cm)
- weight (kg)
- body mass index (BMI,  $\text{kg}/\text{m}^2$ )
- body mass index ( $<30 \text{ kg}/\text{m}^2$  vs  $\geq 30 \text{ kg}/\text{m}^2$ )

- BSA ( $\text{m}^2$ ; DuBois formula where  $\text{BSA} [\text{m}^2] = \text{Weight} [\text{kg}]^{0.425} \times \text{height} (\text{cm})^{0.725} \times 0.007184]$ )
- serum androstenedione
- HOMA-IR
- total fat mass (kg)
- percent total fat mass (%)
- total daily glucocorticoid dose adjusted for BSA (mg/ $\text{m}^2$ /day; in hydrocortisone equivalents [see Appendix 16.3])
- total daily glucocorticoid dose (mg/day; in hydrocortisone equivalents [see Appendix 16.3])
- total daily glucocorticoid dose categories adjusted for BSA (<20 mg/ $\text{m}^2$ /day vs.  $\geq 20$  mg/ $\text{m}^2$ /day; in hydrocortisone equivalents [see Appendix 16.3])
- glucocorticoid type (hydrocortisone alone; prednisone, prednisolone, methylprednisolone, with or without hydrocortisone; dexamethasone, with or without another glucocorticoid)
- glucocorticoid type – dexamethasone use (subjects on dexamethasone at baseline versus subjects not on dexamethasone at baseline)
- glucocorticoid type – hydrocortisone vs. synthetic glucocorticoids (subjects on hydrocortisone alone versus subjects on prednisone [or equivalent] or dexamethasone)
- glucocorticoid type (hydrocortisone; prednisone, prednisolone, methylprednisolone; dexamethasone; note that subjects can contribute to more than one category if taking more than one type of glucocorticoid)
- total daily fludrocortisone dose ( $\mu\text{g}/\text{day}$ ; for subjects taking fludrocortisone)

Stratification factors as entered in the IRT:

- total daily glucocorticoid dose adjusted for BSA category (<20 mg/ $\text{m}^2$ /day vs  $\geq 20$  mg/ $\text{m}^2$ /day; in hydrocortisone equivalents)
- glucocorticoid type (hydrocortisone alone; prednisone, prednisolone, methylprednisolone, with or without hydrocortisone; dexamethasone, with or without another glucocorticoid)
- sex

## 7.4. CAH History

### 7.4.1. CAH Medical Conditions of Interest

A summary of the number and percentage of subjects with each medical condition of interest (“Yes”/ “No”; as specified on the “Conditions of Interest” eCRF) at study entry will be summarized by DB treatment group and overall. For conditions that are sex-specific, the denominator will be based on the number of subjects of that sex within the treatment group.

CAH medical conditions of interest include:

- Impaired fasting glucose
- Impaired glucose tolerance

- Diabetes
- Hypertension
- Hypertriglyceridemia
- Hyperlipidemia
- Osteopenia
- Osteoporosis
- Fragility fracture (not due to trauma)
- Depression
- Anxiety
- Hirsutism (female subjects only)
- Acne (female subjects only)
- Testicular adrenal rest tumors (male subjects only)

#### **7.4.2. CAH Medical History**

CAH medical history at study entry will be summarized by DB treatment group and overall using descriptive statistics. For conditions that are sex-specific, the denominator will be based on the number of subjects of that sex within the treatment group.

- CAH history assessments include:
- Age at CAH diagnosis
- How the CAH diagnosis was made
- Lifetime total number of adrenal crises (requiring hospitalization and parenteral glucocorticoid administration)
- Number of (lifetime) adrenal crises related to stopped/decreased glucocorticoid medication
- Causes of adrenal crises
- Number of adrenal crises within the past 10 years (requiring hospitalization and parenteral glucocorticoid administration)
- Number of adrenal crises within the past 10 years related to stopped/decreased glucocorticoid medication
- Number of adrenal crises within the past 5 years (requiring hospitalization and parenteral glucocorticoid administration)
- Number of adrenal crises within the past 5 years related to stopped/decreased glucocorticoid medication
- Number of adrenal crises within the past year (requiring hospitalization and parenteral glucocorticoid administration)
- Number of adrenal crises within the past year related to stopped/decreased glucocorticoid medication
- Age at menarche (female subjects only)
- Menstrual cycles occurring every 21-35 days (Y/N; female subjects of childbearing potential only not on hormonal or IUD contraception)

## **7.5. Medical History**

Medical history data will be summarized descriptively for the FAS, by treatment group and overall. Medical history data will be coded using MedDRA. The medical history data will be summarized with frequencies and percentages of subjects with at least one medical history item, and subject frequencies and percentages according to the System Organ Class (SOC) and Preferred Term (PT) levels. The table will be sorted alphabetically by SOC and then, within a SOC, by PT.

## **7.6. Summary of Analysis Sets**

A summary of the number and percentage of subjects included in the full analysis set, the full analysis set excluding site number 1083, the DB period safety analysis set, the OL period safety analysis set and the PK analysis set will be provided by DB period treatment group and overall. The number and percentage of subjects excluded from each analysis set by reason for exclusion will also be provided.

## 8. PHARMACOKINETICS

The plasma concentrations of crinecerfont and its metabolites will be summarized with descriptive statistics by nominal visit and nominal time postdose in the DB period. This summary will be repeated for all plasma concentration values collected in the OL period.

All below the lower limit of quantification (BLQ) values (crinecerfont < 5.00 ng/mL; metabolites < 0.500 ng/mL) will be set equal to zero (0) in the plasma concentration summaries. If a subject receives incorrect study drug at any point during the study, the subject's plasma concentration values will be excluded from the summaries that are directly impacted by the incorrect administration and will be documented in the CSR.

The details of the population PK analysis will be described separately and the results provided in a separate report.

## 9. EFFICACY – DB PERIOD

[figure not shown]
The efficacy endpoints and planned analysis methods for the DB period are described below. Unless otherwise specified, the FAS will be used for all efficacy analyses and descriptive statistics.

### 9.1. Multiple Comparisons and Multiplicity

The testing procedure described below will be used to control the familywise Type I error rate for the primary and key secondary endpoints (Figure 1). The promising zone method as planned in this study was shown to not inflate the type I error, as described in the simulation report attached to the Adaptation Plan. All significance levels noted below are 2-sided. All other p-values will not be adjusted for multiplicity and should be considered as nominal p-values.

- The primary endpoint will be tested using a significance level of 0.05.
- If the primary endpoint is statistically significant, then the first 2 key secondary endpoints will be tested using an unequal allocation of significance levels. The change from baseline at Week 4 in androstenedione will be tested using a significance level of 0.02. The achievement of a reduction in glucocorticoid daily dose to physiologic levels ( $\leq 11 \text{ mg/m}^2/\text{day}$  hydrocortisone equivalent adjusted for BSA) will be tested using a significance level of 0.03.
- The family of remaining key secondary endpoints will be tested using the Holm procedure (Holm, 1979). The significance level for this family of endpoints will be dependent on whether the first 2 key secondary endpoints are statistically significant (Wiens, 2003). If both are statistically significant, then the significance level for this family of endpoints will be 0.05. If only one is statistically significant, then the significance level for that endpoint will be used for this family of endpoints. If neither is significant, then this family of endpoints will not be tested for statistical significance. However, nominal p-values will be produced.

**Figure 1: Procedure to Control for Multiple Comparisons**

## 9.2. Statistical Models

### 9.2.1. ANCOVA - continuous endpoints

The continuous efficacy endpoints will be analyzed using an analysis of covariance (ANCOVA) model, which includes the change (or percent change) from baseline to the respective postbaseline visit where the endpoint is being evaluated. The model will include the relevant baseline value as a covariate, treatment group (crinecterfont 100 mg bid; placebo), and stratification factors used in the randomization. Values of the stratification factors entered during randomization in IRT will be used in the primary analysis methods. Any corrected values as reported in the eCRFs for the stratification factors may be used in any supplementary or exploratory analyses and will be stated as such.

An example of the SAS software code is provided below. Note that the PROC MIXED statements shown in this section will be accompanied by additional statements to create and output the required statistics.

```
PROC MIXED;  
CLASS SEX GC_TYPE GC_DOSE TRTP;  
MODEL CHG = TRTP BASE SEX GC_TYPE GC_DOSE;  
RUN;
```

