5.3. Study and Dose Rationale

The present Phase 3 randomized, double-blind, placebo-controlled study is designed to evaluate the efficacy, safety, and tolerability of crinecerfont regimen of 100 mg administered twice daily (bid) in adult subjects with classic CAH due to 21-hydroxylase deficiency. Repeated total daily doses in the range of 100 mg to 300 mg, including bid dosing, have been well tolerated in Phase 1 and Phase 2 studies. Exposure-response analysis using data from the administration of crinecerfont prior to a corticotropin releasing factor-challenge test in healthy subjects and simulations of crinecerfont plasma concentrations following various dose regimens suggest that a

crinecerfont dose of 100 mg bid will result in sustained CRF₁ receptor antagonist activity over the entire day. These data are supported by the results of Study NBI-74788-CAH2001, where subjects with classic CAH received crinecerfont 50 mg at bedtime, 100 mg at bedtime, 100 mg every evening (qPM), or 100 mg bid. This study demonstrated that administration of 100 mg bid crinecerfont led to meaningful median reductions in ACTH and 17-OHP (54% to 75% from baseline) as well as androstenedione concentrations in subjects with classic CAH after 14 days of treatment. A dose-response for androstenedione was observed with approximately 20% median reduction from baseline with the 50 mg dose, approximately 40% with each of the 100 mg once daily doses, and approximately 60% with the 100 mg twice daily dose. Crinecerfont was well tolerated at all dose regimens evaluated. Adverse events were mostly mild, with 1 SAE of cholelithiasis that occurred 34 days after the last dose of study drug and was assessed as unrelated to study drug reported in a subject receiving 100 mg at bedtime. Adverse events reported in 2 or more subjects included headache, upper respiratory tract infection, fatigue, contusion, insomnia, nausea, and viral upper respiratory tract infection. There were no safety concerns related to laboratory, vital signs, or ECG results.

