13.4. Sample Size Determination

The protocol-specified sample size of 165 subjects (110 in the crinecerfont treatment group and 55 in the placebo group) is based on a power calculation for the primary endpoint and considerations for the size of the safety database. Based on a 2-sample t-test, an effect size of 0.75 with a sample size of at least 90 subjects (60 in the crinecerfont treatment group and 30 in the placebo treatment group) will have greater than 90% power to detect a treatment difference at a 0.05 level of significance. With the full sample size of 165 subjects, there is greater than 90% power to detect an effect size as small as 0.55.

To mitigate against the uncertainty of sample size assumptions, an interim analysis is planned to evaluate the study to stop early for futility, increase the sample size, or continue the study as planned. The decision to increase the sample size will be based on the conditional power calculated at the interim analysis and could result in an increase of the planned sample size up to a maximum of 210 subjects (see [Section 13.7](#)).

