### **3. STUDY DESIGN**

This is a Phase 3, randomized, double-blind, placebo-controlled study to evaluate the efficacy, safety, and tolerability of crinecerfont versus placebo administered bid with breakfast and the evening meal (doses separated by approximately 12 hours) for 24 weeks in approximately 165 adult subjects with classic congenital adrenal hyperplasia (CAH) due to 21-hydroxylase deficiency. Eligible subjects will be randomly assigned in a 2:1 ratio (active:placebo) to 2 treatment groups, crinecerfont 100 mg bid or placebo. After the 24-week randomized treatment period, there will be a 6-month, open-label treatment period, during which all subjects will receive crinecerfont 100 mg bid. At Month 12, subjects who have not reduced their glucocorticoid dose to  $\leq 11 \text{ mg/m}^2/\text{day}$  will be re-randomized (2:1) to receive 100 mg every morning (qAM) and 200 mg every evening (qPM) or to continue 100 mg bid, in a blinded fashion. Subjects who have reduced their glucocorticoid dose to  $\leq 11 \text{ mg/m}^2/\text{day}$  will continue to receive 100 mg bid in an open-label fashion. At Month 18, subjects will review applicable portions of the informed consent form and confirm whether they will participate in the optional open-label extension (OLE) treatment period for continued access to crinecerfont. Starting at Month 18, all subjects who are continuing in the OLE will initially receive crinecerfont 100 mg bid. If the subject has inadequate disease control despite receiving glucocorticoid treatment at their target dose (in the opinion of the investigator), the crinecerfont dose may be increased to 100 mg qAM and 200 mg qPM. After the Month 24 visit, an alternative dosing regimen of once daily 200 mg qPM can be considered per the investigator. Subjects will remain in the OLE until crinecerfont becomes commercially available, the Sponsor elects to discontinue development of crinecerfont for CAH, the Sponsor elects to discontinue the study, or the subject meets one of the study withdrawal criteria. A final study visit will be conducted approximately 4 weeks after the last dose of study drug.

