### **3.3. Sample Size Considerations**

The protocol-specified sample size of 165 subjects (110 in the crinecerfont treatment group and 55 in the placebo group) is based on a power calculation for the primary endpoint and considerations for the size of the safety database. Based on a 2-sample t-test, an effect size of 0.75 with a sample size of at least 90 subjects (60 in the crinecerfont treatment group and 30 in the placebo treatment group) will have greater than 90% power to detect a treatment difference at a 0.05 level of significance. With the full sample size of 165 subjects, there is greater than 90% power to detect an effect size as small as 0.55. Sample size and power estimates were obtained from nQuery® Advisor Version 8.

A single planned interim analysis detailed in Section 5.1, with a futility analysis and an unblinded sample size re-estimation, will be performed when approximately the first 76 randomized subjects (approximately 46% of the planned number of enrolled subjects) have had the opportunity to be assessed for the primary endpoint. The unblinded sample size re-estimation may result in an increase of the overall sample size to a maximum of 210 subjects.

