### **9.3.3. Sensitivity Analyses of the Primary Efficacy Results**

The assumptions relative to the ANCOVA model (e.g. linearity, normality) specified for the primary analysis of the primary endpoint will be checked and any violations of these assumptions will be handled through non-parametric statistical methods.

A tipping point sensitivity analysis will be performed to assess the robustness of the missingness assumptions. This sensitivity analysis is based on “delta adjustments” which is a commonly used approach to assess the impact of missing data in clinical trials (O’Kelly and Ratitch, 2014). The imputed Week 24 glucocorticoid daily dose values (from the MI procedure described in Section 16.1) for subjects in either the crinecerfont treatment group or the placebo treatment group will be delta-adjusted (with a range of plausible penalties for each treatment group) until the treatment difference at Week 24 is no longer statistically significant. The implementation procedure for the tipping point analysis is described in Appendix 16.4. The combinations of delta adjustments that tip the result from statistically significant to insignificant along with the corresponding insignificant p-values will be presented in a table and may be presented in a figure.

A complete-case sensitivity analysis will also be performed to test the robustness of the multiple imputation procedure. The ANCOVA analysis for the primary endpoint will be repeated using only subjects with observed data at Week 24. Subjects who are missing the Week 24 primary endpoint will be excluded from the analysis.

Descriptive statistics and LS means for the sensitivity analyses will be presented by treatment group along with the LS-mean treatment difference, 95% confidence intervals, and nominal p-values.

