## **9.4. Analysis of Key Secondary Efficacy Endpoints**

### **9.4.1. Serum Androstenedione**

The first key secondary endpoint is the change from baseline in serum androstenedione at Week 4. The pre-morning glucocorticoid dose androstenedione values at baseline and Week 4 will be used in the calculation of this endpoint (as defined in Section 6.3.4). If a subject is missing their baseline or Week 4 pre-glucocorticoid dose androstenedione value, then the post-glucocorticoid androstenedione values at baseline and Week 4 will be used instead. The primary analysis of this endpoint will be performed using an ANCOVA model as described in Section 9.2.1. Subjects who are missing all androstenedione levels at Week 4 will have their Week 4 data imputed through the multiple imputation procedure described in Section 16.2.

Statistical significance for the treatment comparison will be determined using the multiple comparison procedure described in Section 9.1. Descriptive statistics and LS means will be presented by treatment group along with the LS mean treatment difference, 95% confidence intervals, and p-value.

Descriptive statistics will be presented by treatment group and visit for the serum androstenedione observed and change from baseline values through Week 24. For visits where androstenedione is collected more than once (e.g., Day 1), each visit will be presented with the pre- and post- morning GC dose androstenedione values. The androstenedione observed values from the two screening visits and the average of these values will also be summarized.

Mean ( $\pm$ SEM) values of serum androstenedione at each visit will be summarized in line graphs by treatment group. For visits where androstenedione is collected more than once, each visit will be presented with the pre- and post- morning GC dose androstenedione values on separate plots. Similar graphs will be presented for the changes from baseline.

A tipping point sensitivity analysis of change from baseline in serum androstenedione at Week 4 will be performed to assess the robustness of the missingness assumptions as was described for the primary endpoint in Section 9.3.3. The implementation procedure for the tipping point analysis is described in Appendix 16.5 for each key secondary efficacy endpoint.

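### The confidence interval for Week 4 androstenedione relies on equal residual variance in two arms of unequal size; it may under-cover if the drug effect is proportional, and the SAP provides no robust standard error

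*SAP*

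**What the plan says.** SAP 9.2.1 gives a common model for the continuous efficacy endpoints: "MODEL CHG = TRTP BASE SEX GC_TYPE GC_DOSE". It has no treatment-by-baseline term. The code is offered as an example that "will be accompanied by additional statements to create and output the required statistics", and neither the code nor the text mentions arm-specific variances or a robust standard error. PROC MIXED run this way estimates one residual variance.

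SAP 9.4.1 applies this to the first key secondary endpoint, absolute change in serum androstenedione at Week 4: "The primary analysis of this endpoint will be performed using an ANCOVA model as described in Section 9.2.1". It reports the least-squares mean difference with a 95% confidence interval. SAP 9.1 tests the endpoint at two-sided 0.02.

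Subjects are "randomly assigned in a 2:1 ratio (active:placebo"), which at the planned size means "110 in the crinecerfont treatment group and 55 in the placebo group" (Protocol 13.4; SAP 3.3 agrees).

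SAP 9.3.3 says the ANCOVA assumptions "specified for the primary analysis of the primary endpoint will be checked", with linearity and normality as examples and unspecified non-parametric methods as the fallback. SAP 9.4 has no such check for any key secondary endpoint. The supplementary androstenedione analyses in 9.4.1 (percent change, a different baseline, multiples of the upper limit of normal) all keep the ANCOVA.

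On the expected effect, Protocol 5.3 cites 14-day Phase 2 data with a median androstenedione reduction of "approximately 60% with the 100 mg twice daily dose".

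**The concern.** With 2:1 allocation, the model-based standard error of a treatment difference is right only if residual variances are equal in the two arms. If they differ, pooling gives most weight to the variance of the larger arm, whereas the true standard error depends most on the variance of the smaller arm.

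A drug that lowers a hormone by a roughly constant proportion shrinks its absolute spread as well as its mean. Week 4 values would then be less dispersed on crinecerfont, and the noisier arm would be placebo, the smaller one. The pooled standard error would be too small and the reported interval too narrow. At stake is the stated precision of the hormone effect for the first alpha-controlled key secondary endpoint. The risk of a false claim of effect is not at stake.

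**Working it through.** **The plan's own figures.** The documents give no coverage or variance figure for androstenedione. Their only relevant calculation is power for the primary endpoint, which reproduces. With z = d × √(n₁n₀/(n₁+n₀)):
- 60:30, d = 0.75: 0.75 × √20 = 3.354; power = Φ(3.354 − 1.960) = 91.8% (91.3% by t).
- 110:55, d = 0.55: 0.55 × √36.67 = 3.330; power = Φ(3.330 − 1.960) = 91.5% (91.2% by t).

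Both agree with the stated figure of more than 90%. This calculation assumes a common SD and says nothing about Week 4 androstenedione.

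**Large-sample effect of pooling at 2:1.** Let m be the placebo sample size, 2m the active sample size, and vA and vP the arm residual variances.
- Pooled variance = (2vA + vP)/3, so model SE² = (vA + vP/2)/m.
- True SE² = (vA/2 + vP)/m.
- Ratio R = √[(vA + vP/2)/(vA/2 + vP)]; coverage = 2Φ(1.96R) − 1.

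Example, placebo SD twice active SD (vA = 1, vP = 4): R = √(3/4.5) = 0.816; coverage = 2Φ(1.600) − 1 = 89.0%.

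| Placebo:active residual SD | Coverage of nominal 95% CI |
|---|---|
| 0.5 | 98.4% |
| 0.67 | 97.4% |
| 1.0 | 95.0% |
| 1.25 | 93.1% |
| 1.5 | 91.5% |
| 2 | 89.0% |
| 3 | 86.4% |
| infinite | 83.4% |

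The limit from pooling alone is therefore 83.4%. Lower values also need a skewed baseline.

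**Simulation of the SAP model at 110:55.** Assumed, because the documents do not give them: lognormal baseline with log-SD 0.5, 0.8 or 1.0; a multiplicative treatment effect; log-scale Week 4 noise as shown. Results are ordered by baseline log-SD 0.5 / 0.8 / 1.0. HC3 is a heteroscedasticity-consistent variance. The last column adds an arm-specific slope, evaluates the effect at the overall baseline mean and adds a variance allowance for estimating that mean.

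| Fall; noise placebo, active | Planned CI | HC3, planned model | Interaction + HC3 |
|---|---|---|---|
| None; 0.5, 0.5 | 95.2 / 94.5 / 95.2% | 95.5 / 95.9 / 96.7% | 95.5 / 96.1 / 96.4% |
| 30%; 0.5, 0.5 | 91.6 / 91.0 / 91.8% | 94.5 / 93.2 / 93.3% | 95.0 / 95.0 / 94.8% |
| 60%; 0.5, 0.5 | 88.0 / 83.8 / 81.3% | 94.3 / 90.5 / 87.9% | 95.4 / 92.3 / 92.2% |
| 60%; 0.4, 0.8 | 94.0 / 92.6 / 90.0% | 95.2 / 93.5 / 91.4% | 96.0 / 95.3 / 94.5% |
| 60%; 0.4, 1.0 | 95.4 / 94.6 / 93.2% | 95.4 / 94.5 / 92.9% | 96.1 / 96.2 / 95.7% |
| 40%; 0.4, 0.8 | 96.1 / 96.0 / 95.7% | 95.8 / 95.8 / 94.7% | 96.1 / 96.7 / 96.6% |

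Over a wider grid with equal log-noise (0.3-0.8), planned coverage was 88.5-93.2% for a 30% fall, 85.0-90.2% for 45% and 79.9-88.0% for 60%. Responder/non-responder mixtures gave 93.9-98.0%.

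**What drives it.** Different slopes (0.7 and 0.3) with equal residual SD cost under one point (94.5%), so unequal variance is the main cause. At 1:1 (83:82) the 60% fall with noise 0.5 in both arms gave 93.4% and 91.3% (baseline log-SD 0.5 and 0.8), against 88.0% and 83.8% at 2:1. With no treatment effect, planned coverage was 94.5-96.3% across all settings.

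Multiple imputation was not simulated because the documents state no dropout rate.

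**The case against.** The strongest objection is that the documents say nothing about spread. They give no androstenedione SD, no baseline-to-Week 4 correlation and no arm variances, only an approximate median fall after 14 days. A spread on crinecerfont that is 0.4 of the placebo spread requires every subject to fall by about the same proportion with equal relative noise. The protocol itself expects uneven response: at Month 12 it re-randomizes subjects who have not responded adequately (judged on glucocorticoid dose), and the full analysis set keeps everyone regardless of adherence. Both tend to widen the active arm. This stands. A reader might infer from the proportional scenarios that the interval is too narrow and truly covers 81-93%; that figure comes from assumed variances and is not a property of the plan.

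A second objection is that little depends on this. With a 60% fall and equal log-noise, the planned test rejected in 99.6-100% of simulated trials, so the decision at 0.02 hardly changes. That also stands, and limits the point to the width of an interval.

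A reader might go further and infer that the primary endpoint's standard error is too wide, or that HOMA-IR loses power on the raw scale. The documents supply no variance for the first, and no distribution or expected effect for the second, so neither is claimed here.

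What the objection does not remove is that the planned standard error depends on an equality the sponsor has no stated basis for, and that no safeguard in the SAP covers this endpoint.

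**Conclusion.** The point holds conditionally. If the androstenedione effect is proportional (falls of 30-60%) with similar relative noise in both arms, the nominal 95% interval may cover only about 80-93%. If crinecerfont response is sufficiently more variable, coverage is about 94-98%; intermediate settings, such as a 60% fall with active log-noise twice placebo and a skewed baseline, fall to about 90-94%. The documents cannot say which case applies, so the direction of the error is open.

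It would be wrong to read this as an inflated false-positive rate: under no effect coverage is close to 95%, and the gatekept test keeps its level. The case for change is that a robust standard error moved coverage towards 95% where the planned interval was too narrow and stayed near 95% where it was not.

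**What to change.** In SAP 9.2.1, specify HC3-type standard errors for the continuous endpoints. Preferably add treatment by baseline, centred at the overall baseline mean, and report the treatment difference at that mean. State that the variance allows for estimating the baseline mean: the interaction results above include this allowance, and repeating the simulation without it gave little gain over HC3 on the planned model. Use the same standard error in each imputed dataset (SAP 16.1 and 16.2), in the tipping-point runs and, because 9.2.1 also serves the primary endpoint, in the stage-wise statistics of SAP 5.1.

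The mean-difference estimand does not change. The cost is a small SAP and code change and a slightly wider interval in some settings. The repair is incomplete when baseline is strongly skewed: expect about 90-94%, and 87.9% in the worst setting above if HC3 is used without the interaction.

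A log-scale ANCOVA of Week 4 androstenedione, reported as a ratio to placebo, covered 94-96% in the settings examined and may be added as a supplementary analysis. It should not replace the planned one, because it targets a geometric-mean ratio. It also needs matching rules: SAP 16.2 sets no lower bound on imputed values, so some might not be loggable, and any tipping-point analysis on that scale would need replacements for the additive nmol/L shifts in Table 11.
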